3.2 Inclusion criteria

In order to be eligible to participate in this study, a patient must meet all of the following criteria: 1) aged between 25 and 84 years, 2) using atypical antipsychotic medication for at least 3 months at baseline, 3) the atypical antipsychotic medication is prescribed by the general practitioner, and 4) a 10-year cardiovascular risk of at least 5% at baseline (moderate to severe risk).

3.3 Exclusion criteria

A potential patient who meets any of the following criteria will be excluded from participation in this study: 1) diagnosis of dementia or organic psychosis, 2) diagnosis of cardiovascular disease (acute myocardial infarction, acute coronary syndrome, heart failure, ischemic stroke, transient ischemic attack, peripheral artery disease, aortic aneurysm or a revascularization procedure, i.e. percutaneous coronary intervention or coronary artery bypass grafting).

3.4 Sample size calculation

The sample size calculation is based on the following findings and expectations. Our pilot showed a reduction of the mean QRISK3 score of 1.9 points. This was after a follow-up period of 3 months, and under suboptimal intervention conditions, e.g. unclear expectation management, modified information meeting due to the corona pandemic. The standard deviation of the difference of QRISK3 score was 3.4 and the standard deviation of a single measurement was 12. This means there is a high reliability on patient level.

$$r_s = 1 - \frac{(SD_{diff}/SD)^2}{2} \approx 0.95$$

We expect that in the trial, after optimisation of the TACTIC procedures, we will be able to detect a reduction of a clinically relevant mean QRISK3 score of 2.5 points in the intervention group, compared to the control condition. Given an SD of 12, an intraclass correlation (ICC) of 0.10, and an α of 0.05, 500 simulated trials indicate that 32 general practices with each 12 patients are needed to provide a power of at least 80%. Given drop-out rates of 20% observed in our pilot study and less than 10% in a UK primary care study evaluating a comparable intervention (15), we include 15 patients per cluster. The required total number of participants will be 480 patients in 32 (or more) clusters.

This calculated sample size has also enough power to detect a clinically relevant improvement of 5 points on de mental health inventory, the mental domain of the SF36, which will be our second primary outcome.

4. TREATMENT OF SUBJECTS

Investigational treatment

A transmurale taskforce in the region of Arnhem has previously developed the TACTIC intervention. This taskforce consists of all relevant stakeholders: patients with lived experience from the patient organization 'Vitale Verbindingen', general practitioners from the primary care group 'Onze Huisartsen', psychiatrists from 'Pro Persona' and 'GGNet', mental health nurses from primary and secondary care (including addiction care), pharmacists, life style coaches and members of the municipal social welfare team. The TACTIC intervention has been tested in a recent pilot study which provided valuable input for improving the feasibility and effectiveness of the intervention. We followed the Medical Research Council framework for developing and evaluating complex interventions (16).

TACTIC is a one-time intervention that takes place in the general practice setting. It entails three consecutive steps in addition to usual care, i.e. regular cardiovascular risk management programmes:

Step 1: All participating patients are invited to watch an information video in which they are informed about the multidisciplinary meeting. This information video aims to motivate and prepare patients (and their carers) to participate in the multidisciplinary meeting. The healthcare professionals who take part in the multidisciplinary meeting will introduce themselves and tell about their expertise. After the information video, patients are able to contact their healthcare professional for questions. The information video will take approximately 20 minutes. If desired, patients can meet their pharmacist or the experience expert in advance of the multidisciplinary meeting.

Step 2: A 15-minute multidisciplinary meeting per patient will be held. The general practitioner will open a digital consultation for each patient at least one week before the meeting, enabling the psychiatrist to prepare. When a consultation is initiated digitally, the psychiatrist has access to a part of the electronic medical record of the general practitioner, including diagnosis, medication use, blood pressure, Body Mass Index, and laboratory results. The most recent letter from the psychiatrist will be enclosed (if applicable), together with the results of the Liverpool University Neuroleptic Side Effect Rating Scale (LUNTERS) questionnaire (17), the results of a custom-made questionnaire

on antipsychotic use, and the QRISK3 score at baseline (see Methods 6.1.2. Secondary study parameters).

During the multidisciplinary meeting, the participating patient (and carer), the general practitioner, a psychiatrist, the primary care nurse, and if desired an experience expert (patient coach who lived the experience) will review the patient's antipsychotic use and all other relevant medication (if applicable). Also, possible cardiovascular risk factors will be addressed, such as smoking status, blood pressure, Body Mass Index, blood glucose and cholesterol levels. The multidisciplinary meeting will result in a set of individualised treatment suggestions, including advice on antipsychotic use (e.g. continuation, deprescribing, or switching) and reducing cardiovascular risk.

Step 3: A week after the multidisciplinary meeting, the patient has a consultation with the general practitioner during which the set of individualised treatment suggestions will be translated into an action plan through shared-decision making. This shared-decision making process will benefit the adherence and outcome of the plan. The plan will also define the tasks and responsibilities of the various healthcare providers. Potential actions are altering antipsychotic use, initiating antihypertensive medication or statins, referral to the chronic care nurse (in Dutch: POH-S) for example for smoking cessation, referral to the primary care mental health nurse (in Dutch: POH-GGZ), the dietician, the physical therapist, or a life style coach.

The effects of TACTIC in addition to usual care will be compared to usual care alone, in which patients will be their own comparator, prior to treatment initiation.

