Main study parameters/endpoints: Change in cardiovascular risk, as measured with the QRISK3 score, and change in mental quality of life, as measured with the MHI5 questionnaire.

Nature and extent of the burden and risks associated with participation, benefit and group relatedness:*Burden and risk associated with the intervention:*

Patients who are eligible and who want to participate in the study will be included in the regular cardiovascular risk management programme of the Arnhem primary care cooperative. This programme includes, according to current Dutch guidelines, 1 to 5 consultations with the GP and/or the practice nurse in which physical examination, i.e. measuring blood pressure and body weight, and blood and urine sample collection will take place. The frequency depends on the severity of the cardiovascular risk and the corresponding follow-up period. On top of the regular cardiovascular care patients who participate in the study will also receive the three-step TACTIC intervention. This is a one-time intervention. Patients who are eligible but who do not want to participate in the study will be included in the regular cardiovascular risk management programme, but will not receive the TACTIC intervention.

There is a potential risk associated with participation, as patients whose antipsychotic medication is altered during participation may destabilize mentally. However, this risk is expected to be low. Changes in medication will only take place after this advice has been given in *Step 2* (i.e. multidisciplinary meeting including the patient's GP, a psychiatrist, and the patient self) and has been followed in *Step 3* (i.e. shared decision making between the patient and his/her GP). The advice to change medication will only be given in *Step 2* as the psychiatrist, the GP, and the patient consider this option to be safe. Besides, the advice will only be followed in *Step 3* if both patient and GP feel safe with it. In addition, TACTIC contains precautionary measures to prevent destabilisation, i.e. any change in antipsychotic medication is accompanied with the advice of follow up consultations with the general practitioner or mental health nurse, and all patients who alter their antipsychotic medication will have a crisis prevention plan to ensure safety.

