5.3 Study procedures

After enrolment of the general practice, a list with all eligible patients will be generated in VIPlive. A computerized programme will randomly select 30 eligible patients per general practice, who will receive a letter from their general practitioner, informing the patient about the upcoming trial. Patients will be invited to contact the general practice when they are interested in participation. An appointment for a regular cardiovascular risk management consultation at the general practice will then be made. Patients who did not reply to the letter, will be contacted by phone. In the context of the existing regional cardiovascular risk management programme patients will undergo physical examination (for measuring length, weight and blood pressure), venapuncture and urinalysis (for measuring risk factors, i.e. HbA1c, blood glucose, lipid spectrum and kidney function), and will be asked about their ethnicity, smoking status and family history of coronary heart disease. All other information will be derived from their medical file, e.g. having atrial fibrillation, migraines, or rheumatoid arthritis. In addition to the usual SCORE calculation, the QRISK score will also be calculated specifically for this study. When the QRISK3 score is below 5%, the patient does not meet the inclusion criteria and will be followed by the general practitioner according to the regular cardiovascular risk management

programme. Patients with a QRISK3 $\geq 5\%$ will be invited to sign informed consent for participation in the TACTIC intervention study.

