After signed informed consent and inclusion, baseline measurement will take place and patients will fill in a digital questionnaire using Castor EDC, containing MHI-5, EQ-5D-5L, TIC-P and LUNSERS. As part of the preparation for the multidisciplinary meeting, patients will be asked to fill in a custom-made questionnaire on antipsychotic use. This questionnaire will help healthcare professionals prepare for the meeting and will give the patient insight in possible topics that can be addressed during the meeting. In case patients do not have an email address, we will send the questionnaires by mail. Patients will then watch the information video at home, attend the multidisciplinary meeting, and attend a consultation with their general practitioner, as described in section 5. At five months follow-up, patients will be invited for follow-up (monitoring) measurements at the general practice as part of the regular regional cardiovascular risk management programme (usual care), to undergo physical examination (measuring weight and blood pressure), venapuncture and urinalysis (for measuring risk factors, i.e. HbA1c, blood glucose, lipid spectrum and kidney function). As part of the evaluation, patients will also fill in questionnaires, containing MHI-5, EQ-5D-5L, LUNSERS, TIC-P and general questions about smoking status and family history of coronary heart disease. Depending on which step the cluster has started, patients will undergo one to four follow-up measurements, every five months. This is in line with the routine check-ups patients will have in the regular cardiovascular risk management programme. During the last follow-up measurement, they are also asked to fill in the CSQ-8. Table 1 presents the schedule of assessments.

No diagnostic procedures or treatment will be postponed.

	Visit general practice	Digital information	Physical examination	Laboratory tests	Questionnaires
Week 1 Routine screening and inclusion after informed consent	X		X	X	
Week 2 Baseline measurement					X
Week 3 Information video		X			
Week 4/5	X				

Multidisciplinary meeting					
Week 5/6 Consultation with GP	X				
Month 5 Routine consultation as part of usual care. Follow-up measurement 1 Start Step 2 at Week 1	X		X	X	X
Month 10 Routine consultation as part of usual care. Follow-up measurement 2 Start Step 3 at Week 1	X		X	X	X
Month 15 Routine consultation as part of usual care. Follow-up measurement 3 Start Step 4 at Week 1	X		X	X	X

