7.1 Primary study parameters

As mentioned in chapter 6.1.1, the QRISK3 score is calculated based on several parameters that are collected during regular cardiovascular risk management consultations as part of usual care. For age, we will use age at baseline (T0) at all measurement points. Since the QRISK3 score cannot be calculated when individual items are missing, we will use the following values:

- In case ethnicity is missing, we will use “white or not stated”.

- In case smoking status is missing, we will use “non-smoker”.
- In case the patient is a smoker, but the amount of cigarettes is not stated, we will use “moderate (10-19)”.
- In case cholesterol/HDL ratio is missing, we will use 4.4 for men and 3.7 for women (11). In case systolic blood pressure is missing, we will use the latest measurement of this value, or, if no measurements are available, we will use 129mmHg for men and 123mmHg for women (11).
- In case standard deviation of systolic blood pressure is missing, we will use “0”.
- In case either weight or both length and weight are missing, we will use the latest measurement of the Body Mass Index, or, if no BMI is available, we will use Body Mass Index values as mentioned in table 2.
- In case only length is missing at all measurement points, we will use values as mentioned in appendix ... for calculating Body Mass Index.
- In case calculated Body Mass Index is $<20\text{kg/m}^2$, the value is set to 20kg/m^2 , as the algorithm is not validated for values of Body Mass Index lower than 20kg/m^2 .

Age (years)	Men	Women
25-39	25.2	24.4
40-49	26.2	24.7
50-59	26.5	25.7
60-84	26.8	26.4

Table 2. Mean Body Mass Index (kg/m^2) by age and gender, based on RIVM 2012.

- In case family history of premature coronary heart disease in a first degree relative is “yes” at any measurement point, all measurement points will be set to “yes”, as this factor might not be manifest at the start of enrolment, but does contribute to the patient’s cardiovascular risk, regardless to the moment this factor becomes manifest. This also applies for the factors migraines, rheumatoid arthritis, systemic lupus erythematosus, and erectile dysfunction.
- In case a patient starts blood pressure treatment due to the intervention, all prior measurement points will be set to “yes”, as the indication for blood pressure treatment would have been present provided the patient was on appropriate usual care.

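### For QRISK3, as scheduled, the effect of TACTIC cannot be separated from the effect of entering the regular risk-management programme in patients not already enrolled in it

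*Protocol*

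**What the plan says.** **Comparison claimed.** Protocol Section 4: "The effects of TACTIC in addition to usual care will be compared to usual care alone, in which patients will be their own comparator". The sentence goes on to place the comparator before the start of treatment.

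**Usual care.** The same section says of TACTIC: "It entails three consecutive steps in addition to usual care, i.e. regular cardiovascular risk management programmes". The control condition is thus the programme without TACTIC.

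**Entry into the programme.** The Summary, repeated in Section 8.4, says: "Patients who are eligible and who want to participate in the study will be included in the regular cardiovascular risk management programme". In Section 5.3 an interested patient is booked in as follows: "An appointment for a regular cardiovascular risk management consultation at the general practice will then be made". That visit supplies the QRISK3 value used for the 5% entry threshold.

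**Schedule.** Table 1 puts screening and inclusion in Week 1, baseline questionnaires in Week 2, the video in Week 3, the multidisciplinary meeting in Week 4/5 and the GP consultation in Week 5/6. Follow-ups are at Months 5, 10, 15 and 20. The Month 5 row reads "Follow-up measurement 1 Start Step 2 at Week 1", and Steps 3 and 4 start in the same way at Months 10 and 15. Section 5.3 adds: "Depending on which step the cluster has started, patients will undergo one to four follow-up measurements, every five months".

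**Control condition elsewhere.** Section 6.2.2 speaks of a control period. Section 5.5 makes replacement of a withdrawn patient depend on the condition that patient is in. Neither the text nor Table 1 schedules a follow-up measurement in that period. Figure 1 is not visible in the text available.

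**The concern.** To estimate what TACTIC adds to the programme, some patients must be measured after a time in the programme and before TACTIC. The schedule contains no such measurement. The pre-TACTIC value is taken on the way into the programme, and the next value comes after both.

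The protocol gives its own reasons to expect the programme to matter. The Introduction describes current risk screening in these patients as insufficient, and the Summary expects appropriate screening and management to lower risk. A QRISK3 benefit from programme entry would be credited to TACTIC. Section 8.4 says the cooperative intends regional implementation once feasibility and (cost-)effectiveness are shown, so that decision could rest on the wrong contrast.

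**Working it through.** **1. The plan's own figures.** Section 3.4: 12 / (1 − 0.20) = 15 per cluster and 32 × 15 = 480, which matches. The reliability is 1 − (3.4/12)²/2 = 0.960, against about 0.95 stated. The sample size is not disputed here.

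**2. The layout in Section 5.3 and Table 1.** Step *s* has its baseline at period *s* and is then measured at every later period.

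| Step | Month 0 | 5 | 10 | 15 | 20 | Follow-ups |
|---|---|---|---|---|---|---|
| 1 | C | T | T | T | T | 4 |
| 2 | – | C | T | T | T | 3 |
| 3 | – | – | C | T | T | 2 |
| 4 | – | – | – | C | T | 1 |

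C = before TACTIC, at the programme entry consultation; T = after TACTIC and at least about five months in the programme. This reproduces the one to four follow-ups in the text. There are 4 C cells and 10 T cells, 14 in all. No cell holds patients who have spent time in the programme without TACTIC.

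**3. Can the two effects be separated?** For patients new to the programme, I coded the 14 cells with five period indicators, one TACTIC indicator and one indicator for time already spent in the programme. The matrix has 7 columns and rank 6, because the last two columns are identical. Comparing clusters within a calendar month does not help: at Month 5, for example, Step 2 is just entering while Step 1 has had both. Period adjustment removes secular trend, not programme exposure. The model in Section 7.1 (time, group and their interaction) has no term that could do so.

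**4. Expected estimate.** Let *p* be a constant effect of programme entry, and *q* the share of patients already enrolled, for whom study entry brings no further programme effect. With *q* equal across clusters, the expected estimate is TACTIC effect + (1 − *q*) × *p*. If nobody was enrolled before, the whole of *p* is added. If half were, *p* = 1.0 adds 0.5.

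**5. Illustration of size.** The protocol gives neither *p* nor *q*. I assume a TACTIC effect of 0 and a shift of 0.5 or 1.0 points, which is 20% or 40% of the 2.5-point target. The standard error (SE) is from generalised least squares on cluster-period means with 32 clusters × 12 patients, SD 12, ICC 0.10, fixed periods and random cluster and patient effects. The chance of a significant result is Φ(shift/SE − 1.96) + Φ(−shift/SE − 1.96).

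| Within-patient r | Cluster autocorrelation (assumed) | SE | Shift 0.5 | Shift 1.0 |
|---|---|---|---|---|
| 0.96 | 1.0 | 0.224 | 61% | 99% |
| 0.95 | 1.0 | 0.250 | 52% | 98% |
| 0.95 | 0.9 | 0.457 | 19% | 59% |
| 0.95 | 0.8 | 0.593 | 13% | 39% |

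The nominal rate is 5%. At a cluster autocorrelation of 0.5 the SE is 0.864 and the figures fall to 9% and 21%. These SEs are for a constant treatment effect, which is simpler than the model with interaction in Section 7.1.

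**The case against.** **The layout may not be what Table 1 suggests.** Figure 1, which defines the measured cells, cannot be seen. Sections 5.5 and 6.2.2 presuppose patients in a control condition, and Table 1 could be read as the Step 1 timeline with the other starts marked on it. This stands as a limit on certainty. It does not remove the point: if Figure 1 shows control follow-ups, it disagrees with Section 5.3 and Table 1, and the places must be reconciled.

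**Some patients may already be in the programme.** The Summary says it has run in the region for several years, and inclusion at study entry does not rule out earlier enrolment. This also stands. A reader might infer that every control value precedes the programme and that the whole trial effect is confounded. The documents do not support that. The result in step 3 applies to patients new to the programme, whose share is not given.

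**The comparator is openly stated.** Section 4 says it is the patient's own state before treatment. That is candid about timing, but it still labels that state as usual care, which the same section defines as the programme.

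**Other stronger readings.**
- The blood-pressure recoding rule in Section 7.1 contains the words "provided the patient was on appropriate usual care", which may look like an admission that earlier care was inadequate. It is a condition inside one recoding rule and says nothing general about earlier care.
- Regression to the mean from the 5% entry threshold may also seem important. At a reliability of about 0.95 it is roughly 1 − 0.95 = 5% of the selection differential, too small to carry the argument.
- MHI-5 shares the single pre-TACTIC baseline, but a programme effect on mental quality of life is much less obvious. The point is made for QRISK3 only.

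**Conclusion.** The point holds for QRISK3 on the schedule as written. For patients not already enrolled, the trial estimates TACTIC together with entry into the programme against care before study entry. It does not estimate TACTIC on top of the programme against the programme alone. This follows from the layout and does not depend on any assumed effect size.

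The size of the bias is unknown. Under the stated assumptions (no TACTIC effect, a net programme-entry shift of 0.5 or 1.0 points, cluster autocorrelation 0.8 to 1.0), a significant result would occur in about 13% to 61% or 39% to 99% of trials. These figures illustrate sensitivity and are not estimates of what will happen. The conclusion is conditional on Figure 1 not showing control follow-ups, and it weakens as the share of already enrolled patients rises.

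**What to change.** 1. Reconcile Section 5.3 and Table 1 with Sections 5.5 and 6.2.2, and with Figure 1. State for each step which measurements, if any, are taken in the control condition after study entry. If there are none, reword the objective, the comparison in Section 4 and the planned conclusion: TACTIC delivered together with entry into, or continuation of, the regular programme, against care before study entry.

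2. Record for each patient whether, and since when, they were in the programme before baseline. Pre-specify a supportive QRISK3 analysis by that status. State that the already enrolled subgroup is not randomised, is of unknown size, and gives only supportive evidence on what TACTIC adds.

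The cost is some rewording, one data item and one further analysis. The downside is a less favourable claim. Extracting earlier routine measurements for Steps 2 to 4 is not asked for: with screening described as insufficient, such data would probably be sparse and selective.
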